5.3.3 Criteria and Procedures for Subject Withdrawal from the Study

Clinical trial personnel will collect medical history and verify the inclusion/exclusion criteria of subjects through the hospital's electronic medical record system. Subjects who do not meet the study requirements based on their personal conditions will not be approved to participate in the study.

5.3.3 Subject Loss to Follow-up

Lost to follow-up: Participants did not complete the specified follow-up period but did not 'formally' withdraw from the clinical trial.

If a participant fails to respond to three telephone follow-ups, a registered mail letter must subsequently be sent to the participant. If the participant does not respond to the letter, the participant will be considered as having "lost to follow-up" for current study visits or telephone contacts. The investigator must record this information on the original data sheet. The investigator must report this information to the relevant ethics committee in accordance with the procedures of their institution.

For cases with lost-to-follow-up, the reasons should be explained, and their e-CRF forms should be retained for review. No diagnostic efficacy statistical analysis will be performed, but the patients who undergo examinations may participate in safety analysis as appropriate.

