Visit Plan	For patients under treatment and follow-up at this hospital, no in-person visits are required; relevant data can be obtained from the electronic medical record (EMR) system and imaging system of this hospital. For patients not receiving treatment at this hospital, a telephone follow-up protocol is implemented to obtain relevant pathological results.

research report	The study plans to enroll 120 eligible patients within 3 years, followed up their pathological results, and conduct statistical analysis.
statistical analysis	Statistical analysis was performed using SPSS 17.0. The diagnostic sensitivity, specificity, and negative/positive predictive values were calculated using a four-cell table. The area under the ROC curve and the optimal cutoff value (SUV optimal cutoff) were evaluated by ROC curve analysis. The consistency between 18F-FAPI PET diagnosis and pathological diagnosis was assessed using the kappa test. A p-value <0.05 was defined as statistically significant.

English abbreviation reference

PET	Positron emission tomography
CT	Computed tomography
ROC	Receiver operating characteristic curve
FAPI	Fibroblast activation protein inhibitor

1 Research Background

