5.2.2 Clinical Indicator Assessment

The gold standard is the pathological result of biopsy or surgery.

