5.3 Subject Selection

5.3.1 Eligibility Criteria for Subjects

- (1) Patients with suspected or confirmed lung cancer
- (2) 18F-FAPI PET/CT has been performed.

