8.1 Investigator Data Records

- 1) For all eligible participants who have signed the informed consent form, their relevant data and laboratory test results must be meticulously and thoroughly documented.
- 2) All imaging data were interpreted by two attending physicians with over 5 years of experience in nuclear medicine, and the chief physician provided the final consensus interpretation for any questionable cases.
- 3) Original data records, signed by the investigator and dated.

4) Confirm that all adverse events have been documented, and that serious adverse events have been reported and recorded in accordance with relevant procedures in a timely manner.

9 Expected Research Progress

Study recruitment period: 36 months

Observational study duration: This study was an observational study, with patient mortality serving as the endpoint of follow-up.

10 Adverse Event Assessment and Reporting

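### Protocol 5.3.3 removes patients lost to follow-up from the diagnostic analysis even when their scan and pathology are both on file

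*Protocol*

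**What the plan says.** Section 5.3.3 (Subject Loss to Follow-up) defines loss by contact and completion: "Participants did not complete the specified follow-up period", without formal withdrawal. The operational trigger is a failed sequence of contacts: "If a participant fails to respond to three telephone follow-ups, a registered mail letter must subsequently be sent to the participant". If the letter also goes unanswered, the patient counts as lost. The consequence for analysis is: "No diagnostic efficacy statistical analysis will be performed, but the patients who undergo examinations may participate in safety analysis as appropriate". No exception is made for patients whose pathology is already known.

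The length of the follow-up period is not given in 5.3.3 or elsewhere. Two places bear on it and point in different directions:

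- The synopsis (Visit Plan) says that for patients not treated at the hospital "a telephone follow-up protocol is implemented to obtain relevant pathological results". Its research report row says of the 120 patients that the study "followed up their pathological results, and conduct statistical analysis".
- Section 9 describes an observational study "with patient mortality serving as the endpoint of follow-up".

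On what the primary endpoint requires, section 5.2.2 states: "The gold standard is the pathological result of biopsy or surgery". Section 5.3.1 makes a completed 18F-FAPI PET/CT an entry criterion and admits "Patients with suspected or confirmed lung cancer". Section 6.2 lists recent pathology among the items collected at history-taking.

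**The concern.** A diagnostic accuracy table needs two items per patient: the index test result and the reference standard. Here the first is present at entry by definition, and the second may be present at entry or soon after. Neither depends on the patient answering later calls. Later contact serves the prognosis endpoint (PFS and OS), which is secondary. As written, the rule lets missing data on a secondary endpoint delete complete data on the primary one.

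Three things are at stake. Complete scan-pathology pairs can be lost for no analytic reason. Three centres working from a period with no stated length may not apply the rule alike. And if patients who drop out of contact differ in scan result from those who stay, sensitivity, specificity and accuracy could shift as well as lose precision.

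**Working it through.** **Step 1. What the endpoint needs against what the rule tests**

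| Item | Where | Needed for the four-cell table? |
|---|---|---|
| 18F-FAPI PET/CT result | 5.3.1, entry criterion | Yes |
| Pathology | 5.2.2, gold standard | Yes |
| Completed follow-up period | 5.3.3, period has no stated length | No; serves PFS/OS (2.1.4, 7.3) |

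The rule in 5.3.3 tests only the third row. Because confirmed cases are eligible and recent pathology is collected at history-taking, some patients can hold the first two items before any follow-up contact.

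**Step 2. Two readings of the period**

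- *Synopsis reading:* follow-up is the retrieval of pathology. A lost patient then has no reference standard, and exclusion follows naturally.
- *Section 9 reading:* follow-up ends at death. A patient who becomes unreachable at any time before death is lost, with or without pathology.

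The text of 5.3.3 does not choose between them.

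**Step 3. The plan's own figures**

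Inputs from section 7.1: N = 120; loss 5%-10%, with 10% adopted; sensitivity 0.92; Z = 1.96. The base figure of 113 is reproduced only with sensitivity 0.92 and an allowable error of 0.05: 1.96² × 0.92 × 0.08 / 0.05² = 113.1. The step from 113 to 120 is not reproduced at 10% loss, since 113 / 0.90 rounds up to 126. That is a separate matter, and nothing below depends on it.

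**Step 4. Pairs deleted**

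The protocol does not say what share of lost patients would already have pathology, so 0%, 50% and 100% are assumed.

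- Lost: 0.10 × 120 = 12; 0.05 × 120 = 6.
- Pairs deleted = lost × share with pathology.
- Kept under the rule: 120 − 12 = 108; 120 − 6 = 114.
- Kept if only patients without pathology are left out = kept under the rule + pairs deleted.

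| Loss | Share with pathology (assumed) | Pairs deleted | Kept under 5.3.3 | Kept if only missing pathology excludes |
|---|---|---|---|---|
| 10% | 0% | 0 | 108 | 108 |
| 10% | 50% | 6 | 108 | 114 |
| 10% | 100% | 12 | 108 | 120 |
| 5% | 0% | 0 | 114 | 114 |
| 5% | 50% | 3 | 114 | 117 |
| 5% | 100% | 6 | 114 | 120 |

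**Step 5. Precision of sensitivity**

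Half-width = 1.96 × √(0.92 × 0.08 / n), taking every analysed patient as diseased:

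| n | Half-width |
|---|---|
| 108 | 0.0512 |
| 114 | 0.0498 |
| 117 | 0.0492 |
| 120 | 0.0485 |

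The largest difference, 108 against 120, is about 0.003. Suspected cases are also eligible, so fewer than all patients will be diseased and both half-widths will be larger. If loss is equal in diseased and non-diseased patients, their ratio does not change: √(120/108) = 1.054, about 5% wider at worst.

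Section 7.1 does not say that its 5%-10% covers follow-up to death. If later loss were higher (20% to 50%, purely assumed), 96 to 60 patients would remain, with half-widths from 0.054 to 0.069. The conclusion does not rest on these figures.

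**The case against.** The strongest reply is that the rule was meant only for patients whose pathology was never obtained. The synopsis gives telephone follow-up that single purpose, and patients treated at the hospital are followed through its record systems. So a patient with pathology on file has no described call to miss. The loss allowance in section 7.1 fits this view, because it is added to a sample size calculated for sensitivity, which makes sense if a lost patient is one who cannot be evaluated for the diagnostic endpoint. Section 5.3.3 does not cite section 9, and no passage describes survival calls. On this view the point is one of wording, and its worst-case effect on precision is small.

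Much of this stands. The narrow intent is plausible, the effect on precision is small, and differing practice between centres is a risk rather than a demonstrated fact. It does not remove the problem. The exclusion in 5.3.3 carries no such limit, and its definition rests on completing a period, not on obtaining pathology. The protocol also plans PFS and OS analyses with follow-up to death, which need contact after pathology is known. Nor is this a detail left to the statistical analysis plan: the protocol states the rule, and an analysis plan that kept these patients would depart from it. If the narrow reading is what was meant, the change below only writes it down.

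**Conclusion.** The concern holds. Section 5.3.3 makes inclusion in the primary analysis depend on later contact when it should depend on the presence of the reference standard. Followed as written, it can delete complete scan-pathology pairs: 0 to 12 of 120 at the plan's 10% loss, 0 to 6 at 5%. The cost in precision at these loss rates is at most about 0.003 in the half-width for sensitivity, assuming sensitivity 0.92 and all patients diseased. If loss is unrelated to the scan result, that is the whole effect. If it is related, the estimates could also shift, but the protocol supports neither a direction nor a size, and none is claimed here. The change should be made, because the rule is wrong for this endpoint and cheap to correct. It does not threaten the trial.

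**What to change.** In section 5.3.3 (Subject Loss to Follow-up), replace the clause that bars lost cases from the diagnostic analysis with wording to this effect:

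> Every patient with an evaluable 18F-FAPI PET/CT (read as positive or negative) and a pathology result is included in the diagnostic analysis, regardless of later loss to follow-up. Only patients without a pathology result are left out of the four-cell table, and their number is reported by scan result.

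The safety clause can stay as it is. This wording is sound under either reading of the follow-up period and makes the length of that period irrelevant to the primary endpoint. It does not define the period for the PFS and OS analyses, which remains a separate matter. Reporting the omitted patients by scan result lets a reader judge whether missing pathology is related to the scan. The cost is one clause, with no new procedures, data or patients. It is best settled before outcomes are known, so that the analysis set is not chosen afterwards.

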5.3.4 Selection Time

October 2025 to October 2028, for 3 years.

5.3.5 Number of Subjects Required for Clinical Studies

120 cases

5.4 Study Endpoints

Primary endpoint: Diagnostic efficacy of 18F-FAPI PET/CT in lung cancer patients (sensitivity, specificity, accuracy)

secondary end points:

- ① Compare the diagnostic performance differences of 18F-FAPI PET/CT with CT, MR, and 18F-FDG PET imaging in clinical applications for lung cancer;
- ② Analysis of diagnostic differences in the subgroup of patients (pathological, genetic, etc.) using 18F-FAPI PET/CT;
- ③ Evaluation of 18F-FAPI PET/CT in predicting lung cancer prognosis.

6 Research Procedures and Operational Standards

6.1 Ethical Principles and Informed Consent

Clinical studies shall commence only after the relevant materials have been approved by the ethics committee. During the implementation of the study, any revision to the protocol (excluding administrative aspects) must be re-approved by the ethics committee before the study can proceed.

Prior to the commencement of the study, each investigator obtained written and dated approval/endorsement from the respective IEC for the study protocol (and any amendments), written informed consent, consent updates, and all other written information to be provided to the subjects. The written approval should be indicated, citing the final protocol version number and version date. The composition details of the IEC should be provided to the study sponsor for retention in the main study folder, including the names of the members and their roles within the committee (e.g., Chair, Expert, Founding Member).

During the study period, all documents requiring review should be submitted to the IEC by the study sponsor or investigator in accordance with national regulations.

Informed consent is a measure to protect participants. Prior to the study, investigators must provide detailed information about the clinical study to the participant or their guardian, ensuring full understanding and obtaining informed consent. The clinical study may only commence after the informed consent form has been signed.

6.2 Subject Screening

Participants will sign an informed consent form prior to enrollment in this study. Investigators will explain the nature, purpose, and risks of the study and provide the participants with an informed consent form. Participants will be given sufficient time to consider the significance of the study before deciding whether to participate. Any modifications to the informed consent form must be notified and approved by the ethics committee prior to participant enrollment.

First, participants must undergo an informed consent process and sign an informed consent form. Subsequently, eligible subjects are screened from the target population according to the pre-established inclusion and exclusion criteria of this study, after which they may be considered for inclusion in the research.

Baseline data collection included general examinations, medical history, and laboratory tests conducted at the same hospital or external hospitals within one week prior to the signing of the informed consent form. Adverse events and concomitant medications were collected after the signing of the informed consent form.

history-taking

Conduct a detailed inquiry into the patient's medical history to clarify symptoms, signs, and prior medical history (e.g., tumor history, surgical history, biopsy history, radiotherapy history, chemotherapy history, family history,

allergy history, etc.), relevant laboratory tests, previous imaging findings (including plain radiography, ultrasound, CT, MRI, as well as 18F-FDG PET/CT, PET/MR, etc.), and recent pathological results (including tumor grading and Ki-67 index, etc.), along with the patient's follow-up medical records.

Image judgment criteria

The uptake of imaging agents in tissues or organs that normally do not take up such agents can be considered pathological. Typically, 18F-FAPI is rapidly cleared from the bloodstream. Taking 18F-FAPI as an example, radioactive distribution can be observed in the salivary glands, thyroid, liver, biliary tract, gallbladder, pancreas, adrenal glands, kidneys, intestines, collecting system, and bladder, with almost complete excretion through the biliary tract. There is minimal distribution of the radioactive imaging agent in brain tissue. Compared to the liver, if the uptake is significantly increased in a lesion, it is considered positive, suggesting malignant tumors. Generally, moderate intestinal distribution and non-focal intestinal uptake are considered non-pathological.

Record the primary lesion location, number of metastatic lesions, SUVmax, and tumor volume, among other PET parameters.

7 Statistical Considerations

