1.2 Research Progress of 18F-FAPI PET/CT in the Diagnosis of Lung Cancer

In recent years, 18F-FAPI PET/CT, as an emerging imaging technology, has demonstrated excellent sensitivity and specificity in the diagnosis of lung cancer. Studies have shown that 18F-FAPI PET/CT exhibits significant advantages in detecting lung adenocarcinoma (LAD). A prospective study revealed that 18F-FAPI PET/CT achieved a 100% detection rate for primary tumors. Moreover, in lesions within lymph nodes, pleura, bones, and other tissues, the maximum standard uptake value (SUVmax) of 18F-FAPI was generally higher than that of 18F-FDG. Additionally, 18F-FAPI PET/CT identified more lesions in the detection of lymph nodes, brain, and pleural lesions [3]. These findings indicate that 18F-FAPI PET/CT holds important clinical value in the early diagnosis and staging of lung cancer. Particularly in cases with low 18F-FDG affinity, 18F-FAPI PET/CT provides clearer imaging and higher SUVmax values [4]. Meanwhile, mediastinal and hilar lymph nodes still exhibit a high false-positive rate on 18F-FDG PET, whereas 18F-FAPI PET/CT enhances the specificity of lymph node diagnosis.

Furthermore, 18F-FAPI PET/CT has demonstrated high diagnostic efficacy in the staging evaluation of lung cancer patients. Studies have found that 18F-FAPI PET/CT achieves a diagnostic efficacy of 95.3% in T-stage classification, significantly superior to the 57.1% efficacy of 18F-FDG PET/CT [5]. This difference may be attributed to the specific binding of 18F-FAPI to fibroblast activation protein (FAP) in the tumor microenvironment, which enhances its sensitivity in tumor tissue recognition.

In comparative studies, 18F-FAPI PET/CT has also been found to be a viable alternative to 18F-FDG PET/CT in certain scenarios, particularly for tumors with low 18F-FDG affinity or cases with ambiguous imaging findings. Although 18F-FDG PET/CT remains the preferred imaging modality in specific situations, the potential of 18F-FAPI PET/CT as a complementary imaging approach should not be overlooked [4]. This complementarity offers novel insights into the comprehensive diagnosis of lung cancer, especially in the management of complex cases.

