2.1 Content of Clinical Studies

2.1.1 Evaluation of the Diagnostic Performance of 18F-FAPI PET/CT

This study aims to evaluate the sensitivity, specificity, and accuracy of 18F-FAPI PET/CT in lung cancer patients, providing a basis for clinical application. By performing 18F-FAPI PET/CT scans on lung cancer patients and collecting relevant data, the performance of this modality in early diagnosis, staging, and recurrence monitoring was analyzed. The goal is to provide a scientific basis for clinical decision-making in the diagnosis and treatment of lung cancer.

2.1.2 Comparative Study of 18F-FAPI PET/CT with Other Imaging Techniques (CT, MR, FDG PET/CT)

A comparative study of 18F-FAPI PET/CT versus conventional imaging modalities (CT or MR) or 18F-FDG PET/CT in lung cancer patients, evaluating the differences in tumor detection sensitivity, specificity, and accuracy among various imaging techniques. The study aims to clarify their advantages in clinical applications for lung cancer. The research will focus on analyzing the differences in tumor size, location, metastasis, and pathological characteristics among the imaging techniques, exploring the potential of 18F-FAPI PET/CT in improving diagnostic accuracy and early detection of lung cancer.

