2.1.4 Evaluation of 18F-FAPI PET/CT in Predicting Lung Cancer Prognosis

Based on TNM staging and PERCIST criteria, this study evaluates the post-treatment reassessment, efficacy prediction, and prognostic assessment (AUC comparison of PFS/OS) of 18F-FAPI PET/CT in lung cancer. The research will analyze the monitoring capability of 18F-FAPI PET/CT in assessing tumor response post-treatment

and its value in prognostic evaluation, aiming to provide clinicians with a more precise tool for assessing treatment efficacy. It tracks the time from diagnosis to specific events (e.g., CR, PR, SD, PD, recurrence, death) in lung cancer patients to identify influencing factors. Survival rates over time are plotted using Kaplan-Meier curves to visually compare survival differences across groups. Additionally, Cox proportional hazards model multivariate regression quantifies the contribution of factors such as age and pathological stage to survival risk, aiding clinical decision-making.

3 Mechanism of Action and Research Scope of 18F-FAPI PET/CT

18F (97% β^+ , $T_{1/2}=109.7$ minutes) is currently the most widely used radionuclide in PET/CT due to its chemical, physical, and nuclear properties, making it an ideal choice for peptide-based imaging. 18F-FDG is the most commonly used PET tracer in oncology, serving as the preferred modality for tumor diagnosis and therapeutic efficacy evaluation. However, 18F-FDG PET/CT exhibits relatively low sensitivity and specificity for tumors with low invasiveness, high differentiation, or mucinous tissue, while physiological uptake in organs such as the oropharynx and digestive tract often obscures tumor metabolism and uptake. Additionally, mediastinal and hilar lymph nodes still show a high rate of false positives on 18F-FDG PET, whereas 18F-FAPI PET/CT improves the specificity of lymph node diagnosis. Furthermore, compared to 68Ga-labeled tracers, 18F-labeled FAPI has better resolution potential due to its lower positron energy. Therefore, 18F-labeled FAPI holds significant clinical value and promising prospects.

4 Indications, Contraindications, and Precautions

4.1 Eligibility Criteria: Patients with suspected or confirmed lung cancer who have undergone 18F-FAPI PET/CT

4.2 Exclusion Criteria:

- (1) Concurrent presence of other active malignant tumors or a history of other malignant tumors within the past 5 years;
- (2) Severe uncontrollable diseases or active infections;
- (3) Ineligible participants for informed consent.

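### The CT, MR and FDG comparators for secondary endpoint 1 are opportunistic scans with no required set or interval, so pairing with FAPI is incomplete and the contrast can reflect case mix, disease change or referral pattern instead of accuracy

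*Protocol*

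**What the plan says.** The first secondary endpoint in section 5.4 is: "Compare the diagnostic performance differences of 18F-FAPI PET/CT with CT, MR, and 18F-FDG PET imaging in clinical applications for lung cancer". Section 2.1.2 describes the work as "A comparative study of 18F-FAPI PET/CT versus conventional imaging modalities (CT or MR) or 18F-FDG PET/CT in lung cancer patients" and names sensitivity, specificity and accuracy as the quantities to be compared.

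On who enters and what is collected:

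- **Entry.** Section 4.1 reads "Patients with suspected or confirmed lung cancer who have undergone 18F-FAPI PET/CT". Section 5.3.1 lists suspected or confirmed lung cancer and "18F-FAPI PET/CT has been performed". Neither asks for CT, MR or FDG PET.
- **Exclusions.** Sections 4.2 and 5.3.2 do not exclude earlier anticancer treatment.
- **Study type and data source.** Section 9 states "This study was an observational study". For patients managed at the hospital, the Visit Plan in the synopsis says that "relevant data can be obtained from the electronic medical record (EMR) system and imaging system of this hospital".
- **Comparator scans.** History-taking in section 6.2 covers "previous imaging findings (including plain radiography, ultrasound, CT, MRI, as well as 18F-FDG PET/CT, PET/MR, etc".
- **Time limits.** Section 6.2 sets one week before consent for general examinations, medical history and laboratory tests. No section sets an interval between FAPI and a comparator.
- **Background.** Section 1.2 presents FAPI as a possible alternative to FDG, "particularly for tumors with low 18F-FDG affinity or cases with ambiguous imaging findings".

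**The concern.** An accuracy comparison is interpretable when both tests are applied to the same patients, in the same disease state, and entry does not depend on the result of either test. The protocol secures none of these for the comparators. FAPI exists for everyone by definition, while each comparator exists for whoever happened to have it, and at whatever time.

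If FAPI in the whole cohort is set against FDG, CT or MR in a subset, a difference may come from the kind of patient who had the other scan. If biopsy, treatment or growth falls between the scans, it may come from a change in the lesion. If the comparator result influenced who was sent for FAPI, it may come from referral. The statement in section 2.1.2 that the study explores whether FAPI improves diagnostic accuracy would then lack a sound basis.

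These are matters of eligibility and data collection. A later analysis plan cannot recover a referral reason that was never recorded.

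**Working it through.** The protocol states no figure for this comparison: no comparator sensitivity, no expected number of patients with each comparator, no referral rates. The one sample-size figure (113, section 7.1) concerns a single test's precision and does not bear on this point. The check is therefore mainly a reading of the sections against each other, followed by an illustration.

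**1. Who has each test.** FAPI: all 120 planned patients (5.3.1, 5.3.5). CT, MR, FDG: an unknown number each. Section 5.4 joins the comparators with *and*; section 2.1.2 joins them with *or*. The comparator set can thus differ from patient to patient. A patient with both FAPI and a comparator does give a within-patient pair, so the data are incompletely paired, with a different paired subset for each comparator.

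**2. When the scans were done.** The one-week limit in 6.2 is tied to consent and does not clearly cover imaging, although previous imaging sits under history-taking. Even on the wider reading it is not an interval between two scans. Confirmed cancers are eligible, previous treatment is not excluded, 2.1.1 includes recurrence monitoring, and 6.2 collects biopsy, radiotherapy and chemotherapy history. Biopsy or treatment can therefore lie between the scans.

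**3. What could drive selection, and which way.**
- Section 1.2 makes it plausible that some patients reach FAPI after a negative or unclear scan, mainly FDG. That would lower apparent comparator sensitivity.
- The reference is pathology (5.2.2). If comparator-positive patients are likelier to be biopsied, comparator-detected cancers are over-represented. That would raise apparent comparator sensitivity.
- If comparator-negative patients are preferentially sent to FAPI, non-cancer patients are also enriched for comparator negatives. That would raise apparent comparator specificity.

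**4. Illustration for sensitivity.** Let s be the true comparator sensitivity and r the number of times likelier a comparator-missed cancer is to enter the FAPI cohort than a comparator-detected one. Both are assumptions.

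Apparent comparator sensitivity = s / (s + r(1 − s)).

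With s = 0.85:
- r = 0.5: 0.85 / (0.85 + 0.075) = 0.92
- r = 1: 0.85 / (0.85 + 0.15) = 0.85
- r = 2: 0.85 / (0.85 + 0.30) = 0.74
- r = 3: 0.85 / (0.85 + 0.45) = 0.65

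For the FAPI-minus-comparator difference, take FAPI sensitivity as 0.92 (the planning value in 7.1), so the true difference is 0.92 − 0.85 = 0.07. With *a* the proportion of cancers positive on both tests, *b* = 0.92 − *a* is positive on FAPI only, and

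apparent FAPI sensitivity = (*a* + r·*b*) / (0.85 + 0.15r).

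| r | Difference if errors are independent (*a* = 0.92 × 0.85 = 0.782) | Difference if misses largely coincide (*a* = 0.83, assumed) |
|---|---|---|
| 0.5 | 0.00 | 0.03 |
| 1 | 0.07 | 0.07 |
| 2 | 0.18 | 0.14 |
| 3 | 0.27 | 0.19 |

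Example, r = 2, misses coinciding: FAPI = (0.83 + 2 × 0.09) / 1.15 = 0.878; comparator = 0.739; difference = 0.139.

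These calculations already suppose that every patient has both scans. Pairing alone therefore does not remove this selection, which is why the referral reason also has to be recorded.

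**The case against.** The strongest reply is that every participant has FAPI, so anyone with a comparator has both tests. Restricting to those patients and choosing a paired test are commonly left to the statistical analysis plan, which is not shown. This stands as far as it goes. A reader might infer that the comparison is unpaired, or that section 7.3 dictates a contrast between different patients. It does not: its four-cell formulas are generic and silent on who enters a comparison. What remains is that eligibility and data collection fix neither a comparator, nor an interval, nor a record of why FAPI was ordered.

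A reader might also infer that the cohort is enriched for comparator failures and that the endpoint is therefore biased toward FAPI. The protocol does not support that as a fact. Section 1.2 is literature background and not a referral rule, the synopsis calls FAPI a routine tracer at the lead hospital, and confirmed cancers are eligible. Verification by pathology and the effect on specificity can push the other way.

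Nor do comparators necessarily precede FAPI. Since FAPI has already been done at entry, previous imaging means imaging before history-taking, so the order of the scans is open.

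Finally, the fall in apparent comparator sensitivity is not the bias in the difference between tests. At r = 3 the comparator falls by 0.85 − 0.65 = 0.20, but with largely coinciding misses the difference shifts only by 0.19 − 0.07 = 0.12.

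**Conclusion.** The point holds as a weakness of design and data collection for a secondary endpoint. The comparators are opportunistic scans, pairing is incomplete, the scans are not aligned in time, and each comparator comes from its own self-selected subset. An observed difference can therefore reflect case mix, disease change or referral pattern instead of accuracy.

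Selection in favour of FAPI is plausible, mainly against FDG, but the protocol shows neither its direction nor its size. The figures above rest on an assumed FDG sensitivity of 0.85, assumed values of r, and assumed overlap of errors. They show that the result is sensitive to an unrecorded quantity; they do not estimate a bias. With r = 1 this selection bias disappears, and with r = 0.5 it favours the comparator. The primary endpoint is not affected by this point.

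**What to change.** In sections 2.1.2 and 7.3:

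- Restrict each comparison to patients who have both FAPI and that comparator over the same body region, within an interval that the sponsor fixes in advance, with no biopsy of the lesion or anticancer treatment in between.
- Compare the two tests as matched pairs (McNemar), separately in reference-positive and reference-negative patients, and report the paired number for each comparator.
- Label the endpoint descriptive.

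Add one case report form field for the reason FAPI was ordered, and report results by that reason as a sensitivity analysis. Do not exclude patients from the main comparison because their comparator was negative or equivocal: that selects on the comparator's own result and would inflate its apparent sensitivity.

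The cost is protocol wording and one extra field; no new scans are needed. The downside is that each comparison will rest on fewer than 120 patients.
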